9 STUDY ADMINISTRATION

9.1 Treatment Assignment Methods

9.1.1 Randomization

Participants will be randomized to one of the four condition groups.. A statistician who is not involved with enrolling subjects will be responsible for creating the randomization chart. We will do block randomization for 8 assignments at a time. Each block will contain the four arm assignments repeated once in a random order. We will create a string that is 250 assignments long. As participants reach the intervention phase they will be assigned to the next available assignment in this string. Once an assignment has been used it is no longer available to be used. Study staff and participants will not be blinded to the condition. Individuals conducting data analyses will use data which blinds them to which group participants are in.

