3.1.3 Intervention Period (4 Week Block)

At the beginning of the intervention period (this will start within 2 business days of baseline measurement period survey completion), all participants will receive an email with a link to an educational website that raises awareness of the dangers of distracted driving (<http://endddd.org>). The Children's Hospital of Philadelphia has performed an independent evaluation of the educational content of the website and found it to be evidence based, and scientifically guided⁸.

DriveID will be used as a cellphone blocking device for those in the three cellphone blocking conditions where the phone will lock while driving, but the locking function can be overridden according to pre-set settings. DriveID will continue to monitor cellphone use while driving including how often the teen unlocks the cellphone as well as if they are using the phone for a call or other phone features. However, DriveID is not able to differentiate which phone features are being used.

The study team does not promote texting and driving and encourages all participants to drive safely.

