3.2 Allocation to Treatment Groups and Blinding

Participants will be randomized to one of four groups. The randomization chart will be maintained on a secure server that is only accessible by key study personnel. Participants and study staff will be aware of which group they have been assigned to. A minimum of five participants will be enrolled into each group.

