3.3.2 Total Number of Study Sites/Total Number of Subjects Projected

The study is being conducted at the Children’s Hospital of Philadelphia and the University of Pennsylvania. It is expected that up to 250 people will participate in this research study.

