4.4 Subject Completion/Withdrawal

Participants may withdraw from the study at any time. They may also be discontinued from the study at the discretion of the Investigators at any time.

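### A fixed block size of 8, written into the protocol of an unblinded trial, lets anyone who tracks assignments know one in seven in advance: a minor point with a cheap remedy

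*Combined protocol and SAP*

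**What the plan says.** Section 9.1.1 gives the allocation scheme: "We will do block randomization for 8 assignments at a time". On block content it says "Each block will contain the four arm assignments repeated once in a random order", which on the usual reading means four arms, two copies each, shuffled. On list length: "We will create a string that is 250 assignments long". Each teen takes the next unused place on this single list on reaching the intervention phase. No strata or site-specific lists are mentioned.

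On blinding, the same section says "Study staff and participants will not be blinded to the condition", and Section 3.2 likewise has staff knowing the groups. Three safeguards are stated: the list is made by a statistician who does not enrol participants, data analysts are blinded to group (both Section 9.1.1), and the chart sits on a restricted server (Section 3.2).

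Three other provisions bear on what foreknowledge could do:

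- Section 3.1.3 ties the start of the intervention to the post-baseline survey: "this will start within 2 business days of baseline measurement period survey completion".
- Section 4.4 says of participants: "They may also be discontinued from the study at the discretion of the Investigators at any time".
- Section 6.3.2 defines the primary analysis set as those randomized at the start of the intervention period.

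The plan does not mention varying the block size, keeping it from staff, or what happens to the incomplete last block.

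**The concern.** Concealment needs more than a locked list. When the block size is fixed and known, and past assignments are visible, the remaining places in a block can be worked out by counting. The separate statistician and the restricted server protect the list itself but not against this.

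Late randomization narrows the problem and also changes it. Consent, assent, eligibility and four weeks of baseline come first, so foreknowledge has little bearing on who enrols. By the time of assignment, however, more is known about each teen. Section 4.3.1 allows drive data to be viewed once a drive is over, and Section 9.2.2 allows study team members to upload the data manually. A teen whose entry is delayed could move to a different place on the list. A teen discontinued just before assignment would never enter the analysis set in Section 6.3.2. Blinding the analysts cannot undo a selection made earlier. At stake is the comparability of each blocking arm with control, in a pilot meant to supply data for sizing later trials.

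**Working it through.** **Inputs.** Four arms (Section 3.2: "Participants will be randomized to one of four groups"); block size 8 and list length 250 (Section 9.1.1); staff unblinded (Sections 3.2 and 9.1.1). The plan's block size reproduces: 4 arms × 2 copies = 8.

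**Predictability within a block.** There are 8!/(2!)^4 = 2,520 equally likely orders. For each position, given all earlier assignments in the block:

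| Position | Certain (one arm left) | At least one arm ruled out | Best guess right |
|---|---|---|---|
| 1 | 0 | 0 | 1/4 |
| 2 | 0 | 0 | 2/7 |
| 3 | 0 | 1/7 | 1/3 |
| 4 | 0 | 3/7 | 2/5 |
| 5 | 0 | 27/35 | 31/70 |
| 6 | 0 | 1 | 10/21 |
| 7 | 1/7 | 1 | 4/7 |
| 8 | 1 | 1 | 1 |

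- Certain: (1/7 + 1)/8 = (8/7)/8 = 1/7 = 14.3%.
- At least one arm ruled out: (1/7 + 3/7 + 27/35 + 3)/8 = (152/35)/8 = 19/35 = 54.3%.
- Best guess right: the last column sums to 3.760, and 3.760/8 = 47.0%, against 25% by chance.

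**Over the whole list.** 250 = 31 × 8 + 2. The 31 full blocks give 31 × 8/7 = 35.4 assignments known in advance; the two left over give none.

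**Other readings of the block description.** If each eight were two separate random orders of the four arms, places 4 and 8 would be certain: 2/8 = 25%. If one order of four were used twice, places 4 to 8 would be certain: 5/8 = 62.5%. The 14.3% is the lowest of the three.

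**After the fix.** I simulated 1,500 lists of 248 assignments with block sizes 8, 12 and 16 drawn with equal probability. The observer was assumed to know the three sizes but not their order.

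| | Fixed 8 | Random 8/12/16, set of sizes known |
|---|---|---|
| Certain | 14.3% | about 2.4% (this run 2.45%) |
| At least one arm ruled out | 54.3% | about 12% |
| Best guess right | 47.0% | about 44% |

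If the set of sizes is also unknown, counting gives no certainty. Guessing whichever arm has come up least often so far is still right about 44% of the time.

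**List length.** 250/8 = 31.25, so the list is 31 blocks plus 2 assignments. If it is used up, the arms are 63/63/62/62, or 64/62/62/62 with probability 1/7. The largest difference is 2.

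**The case against.** The strongest reply is that the opening is narrow and the documents show nobody using it. Much of that stands.

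- A reader might infer that staff chase the survey that triggers assignment. The documents do not say so. The study-team reminders in Section 4.3.4 concern the end-of-study survey, and the reminders about incomplete steps in Section 4.1 name no sender.
- A reader might infer that staff can put waiting teens in order within the two business days. Section 3.1.3 says when the intervention starts, not who decides the order. Reordering also needs two or more teens waiting at once, and no enrolment rate is given.
- The documents do not say who sees the running order of assignments. The 14.3% applies to someone who follows all of them.
- The discontinuation clause in Section 4.4 is general and is not aimed at the moment before assignment.
- A reader might infer that any resulting selection would be undetectable. That is too strong. Unlocks are device-recorded for every teen before assignment, Section 6.3.1 summarises baseline characteristics, and the endpoint in Section 6.3.2 is change from baseline. Selection on baseline phone use could be examined by arm and is partly addressed by the endpoint.

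It is also fair that this is a pilot with feasibility as its primary objective, that the outcome is device-recorded, and that the remedy barely changes best-guess accuracy.

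The reply does not dispose of the counting. None of the stated safeguards prevents it, and selection on traits the study does not measure would stay hidden.

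**Conclusion.** The point holds as a minor one. With the fixed block of 8, a person who knows the block size and tracks every assignment on the single list knows 14.3% of assignments beforehand and can rule out at least one arm at 54.3%. This assumes that each block holds two shuffled copies of every arm; the other readings are worse. The consequence is confined to the timing of entry to the intervention phase and to discontinuation just before assignment. These figures measure predictability. They do not measure bias in the treatment comparison, which the documents give no basis to quantify, and nothing in them suggests that staff intend to steer assignments.

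A reader might also take the 250-place list as a flaw in its own right. It is housekeeping only: the arms differ by at most 2, Section 3.3.2 treats 250 as a ceiling ("It is expected that up to 250 people will participate in this research study"), and stopping at any number that is not a multiple of 8 leaves a partial block anyway.

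**What to change.** In Section 9.1.1, replace the fixed block with permuted blocks of randomly varying size (for example 8, 12 and 16). State there only that sizes vary at random, and keep the actual sizes with the list statistician and out of any document that staff hold. Generate whole blocks until the list reaches at least 250. With these sizes every total is a multiple of 4, so the list would end somewhere from 252 to 264. If assignment has already begun, the unused part can be regenerated from a block boundary.

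The cost is one regenerated list and two edited sentences. The downside is a possible between-arm difference of 4 instead of 2 if enrolment stops mid-block, because a block of 16 holds four places per arm where a block of 8 holds two. The gain is in removing certainty and most exclusions of arms; guessing by counting stays well above 25%.

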4.3.2 Intervention

At the completion of the baseline phase, all participants will receive an email to an educational website where they can learn about the dangers of distracted driving (<http://endddd.org>). Teens will also complete a survey.

Cellcontrol will remotely flip the participant's DriveID into a cellphone blocking mode for those in the three blocking conditions of the study on the first day of the intervention period. Teens randomized into the control group will continue with DriveID as is (information regarding cell phone use will continue to be collected, but no blocking will occur). In the blocking conditions, the phone will lock when being used while driving, but the locking function can be overridden.

Coded data on primary and secondary endpoints will be automatically uploaded daily whenever the phone has a Wi-Fi or cellular data connection to the Cellcontrol server and then exported through an encrypted, secure internet connection to Penn's Way to Health IT Platform for management and analysis via linkage of a study ID.

All parents will have the option to check teen's phone use while the vehicle is in motion on the website (<https://account.cellcontrol.com/login.php>) during weeks five to ten. Parents in the opt-out blocking with parental notification group will receive a notification every time the phone is being used while the vehicle is in motion.

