9.2.1 Way To Health

All personal information that the participant is asked to provide will be collected via *Way To Health*. *Way To Health* collects subjects' names, dates of birth, addresses, email addresses, phone numbers, and the last four digits of their social security number. They also request the name and phone number of an alternate contact. To assure that participant confidentiality is preserved, individual identifiers are stored in a single password protected system that is accessible only to study research, analysis and IT staff. The last four digits of participants' social security numbers will be stored in a locked cabinet to be destroyed at a later date. An investigator or statistician who logs in will be able to access only non-identifiable data. The *Way To Health* administrative group and research coordinators responsible for contacting participants for follow-up study visits or responding to questions about the study are able to view participant names and contact information. The WTH web development team and Project Director currently have administrative access to PHI. All of these personnel will have completed Human Subjects Protection and HIPAA privacy training. The system automatically generates logs of all data queries which can be reviewed by research staff to ensure that no unauthorized persons have gained access to identifiable information. This system is hosted on site at The University of Pennsylvania (UPenn) and is protected by a secure firewall and several layers of operational security. Once a participant has been entered into this system, they are given a unique study identification number (ID). Any datasets and computer files that leave the firewall are stripped of all identifiers and individuals are referred to by their study ID. The study ID is also used on all analytical files.

Data will only be transferred through DriveID, Cellcontrol, Penn's Way to Health IT Platform, and the CHOP and Penn study teams. Data will be stored on secure servers both at

CHOP and Penn. Any data transferred between the CHOP and Penn study teams will be transferred via encrypted hard drive or secure email.

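### Does leaving unnamed the holder of the randomization list, and the person who releases each assignment, put allocation concealment at risk?

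*Combined protocol and SAP*

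**What the plan says.** Section 9.1.1 covers how the list is made: "A statistician who is not involved with enrolling subjects will be responsible for creating the randomization chart". On its structure: "We will do block randomization for 8 assignments at a time", each block holding the four arms twice. On its use: "As participants reach the intervention phase they will be assigned to the next available assignment in this string", and an entry once used cannot be used again. On blinding: "Study staff and participants will not be blinded to the condition", although the people who analyse the data work with masked groups.

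Section 3.2 covers custody: "The randomization chart will be maintained on a secure server that is only accessible by key study personnel". The visible text does not list those personnel.

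Five other places bear on the point:

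- Section 3.1.3 starts the intervention period within two business days of the teen completing the post-baseline survey.
- Section 4.3.2 has the vendor remotely switch "DriveID into a cellphone blocking mode for those in the three blocking conditions of the study on the first day of the intervention period".
- Section 4.4 lets the investigators discontinue a participant at their discretion at any time.
- Section 6.3.2 analyses everyone randomized at the start of the intervention period.
- Section 9.2.1 describes access within Way to Health: "research coordinators responsible for contacting participants for follow-up study visits or responding to questions about the study are able to view participant names", whereas "An investigator or statistician who logs in will be able to access only non-identifiable data".

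**The concern.** An independent statistician secures the making of the list. Concealment also depends on who can see the list afterwards and who releases the next entry. The plan restricts the first to an undefined group and describes the second in the passive voice. Coordinators who speak to teens, and investigators who may discontinue them, are not expressly excluded. Staff know past assignments and the block size is stated, so some inference is possible even without the list.

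Two routes would matter if someone knew the next arm and acted on it. One is to change the order of two teens whose two-day start windows overlap. The other is to discontinue a teen just before assignment, which leaves that teen outside the intention-to-treat set. Either could make the arms differ in ways that the covariates in Section 6.3.2 do not capture. It could also distort retention by arm, a feasibility measure in Section 6.2 for which no adjustment is described. At the minimum of five per arm, one teen is 1/5 = 20 percentage points of an arm's retention.

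**Working it through.** The plan states no figure for this point, so there is none to reproduce. The check asks how much could be foreseen, and how often that could alter an arm.

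**Inputs from the documents.** Four arms; blocks of 8 (each arm twice); at least five per group, so 4 × 5 = 20 teens (Section 3.2); up to 250 participants (Section 3.3.2); start within two business days of survey completion (Section 3.1.3).

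**Assumptions.** Even accrual over T = 12 to 24 months, 21 business days a month, and one unstratified list. The documents give no accrual rate.

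**Foreseeing the next arm from the blocks alone.** The observer knows every earlier assignment.
- Position 8 is always certain. Position 7 is certain when the last two entries match, which has probability 1/7. The certain share is (1 + 1/7)/8 = 14.3%.
- The best guess, by exact recursion over the remaining counts, is right 3.7595 times in 8 = 47.0%, against 25% by chance.

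**When a swap would change the arm.**
- Adjacent entries match with probability 1/7 inside a block (seven pairs) and 1/4 across a boundary (one pair). They differ with probability 1 − (7 × 1/7 + 1/4)/8 = 84.4%.
- A certain position 7 is followed by the same arm, so swapping there does nothing. Only position 8 followed by a new block counts: (1/8) × 0.75 = 9.4%.

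**Overlapping start windows.** With r = N/(21T) completions per business day and a wait of w days, the chance that another teen arrives is 1 − exp(−wr). At w = 2 this is 7.6% to 14.7% for N = 20 and 62.9% to 86.2% for N = 250.

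**Product: share of assignments with an opportunity.**

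| Who | Wait | N = 20 | N = 250 |
|---|---|---|---|
| Certain inference from blocks | 2 days | 0.7–1.4% | 5.9–8.1% |
| Opens the list | 2 days | 6.4–12.4% | 53–73% |
| Opens the list | 1 day | 3.3–6.4% | 33–53% |
| Opens the list | half a day | 1.7–3.3% | 18.5–33% |

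The list-access rows apply only if a person who handles teens can open the list, and no passage says so. Two days is the maximum wait in Section 3.1.3. If assignments are released when the survey is completed, every row falls to near zero. The 250 column treats a ceiling on participants as the number randomized. Every entry would still have to be multiplied by the chance that someone acts on a preference, for which the documents give no figure.

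**Reading the passages together.** The coordinator sentence in Section 9.2.1 concerns names and contact details in Way to Health, not the randomization list. The vendor's switch in Section 4.3.2 carries out an assignment already made and reveals nothing about the next one. Start times follow the teen's own survey completion, and Section 9.1.1 then takes entries in sequence. The order is therefore largely fixed by participants, not staff.

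**The case for a change.** The best argument for a change is that concealment should be assured by what is written, not by good conduct. The safeguards named cover creation and storage of the list, while custody and release are left open. By the time of assignment staff may have seen four weeks of driving data, since Section 4.3.1 allows viewing after each drive. They could therefore hold prognostic information. A teen discontinued just before assignment would not appear in the intention-to-treat set. A few sentences would settle the matter at little cost.

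The textual part of this stands: the roles and the releasing step are not named, and discretionary discontinuation before assignment has no stated rate. The inference does not stand. Silence about who holds a restricted list is not evidence that contacting staff hold it. The discontinuation route needs an investigator who knows the next arm, foresees how the teen will behave, and acts on it. The freed entry then goes to the next teen, so the 20-point step in retention appears only if that replacement behaves differently. At 250/4 = 62.5 per arm the step is 1/62.5 = 1.6 points. Varying the block size (4, 8 or 12) would lower the certain share from 14.3% to about 3.6%, but correct guesses would stay near 46%. The largest possible imbalance between two arms would rise from 2 teens to 3.

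**Conclusion.** No change to the plan is needed. This is missing operating detail of the kind that a trial team and its independent statistician settle sensibly when they set up the list. Selection at enrolment, the usual harm from weak concealment, is largely precluded because assignment comes after consent, assent, eligibility and the baseline period. Phone use is recorded by the device, analysts are masked, and the primary objective is feasibility.

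The exposure that rests on facts in the documents (unblinded staff, known blocks of 8) is small where certainty is required: 0.7% to 1.4% of assignments at 20 teens, or 0.14 to 0.28 of a teen. At 250 it is at most about 8%, with every teen waiting the full two days. Guesses short of certainty are right 47.0% of the time and are not counted in those figures. The larger list-access figures depend on access that no passage grants. All of these are opportunities, and the resulting bias cannot be estimated from the documents.

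The conclusion assumes that the people who contact or can discontinue teens do not hold the list, which is the ordinary reading of an independently created, access-restricted list. It would change if records showed otherwise. The usual account of participant flow, with a count of teens who finished baseline but were not randomized, would let a reader check the discontinuation route.

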9.2 Data Collection and Management

Confidentiality, Security, and Anonymization

9.2.1 Way To Health

All personal information that the participant is asked to provide will be collected via *Way To Health*. *Way To Health* collects subjects' names, dates of birth, addresses, email addresses, phone numbers, and the last four digits of their social security number. They also request the name and phone number of an alternate contact. To assure that participant confidentiality is preserved, individual identifiers are stored in a single password protected system that is accessible only to study research, analysis and IT staff. The last four digits of participants' social security numbers will be stored in a locked cabinet to be destroyed at a later date. An investigator or statistician who logs in will be able to access only non-identifiable data. The *Way To Health* administrative group and research coordinators responsible for contacting participants for follow-up study visits or responding to questions about the study are able to view participant names and contact information. The WTH web development team and Project Director currently have administrative access to PHI. All of these personnel will have completed Human Subjects Protection and HIPAA privacy training. The system automatically generates logs of all data queries which can be reviewed by research staff to ensure that no unauthorized persons have gained access to identifiable information. This system is hosted on site at The University of Pennsylvania (UPenn) and is protected by a secure firewall and several layers of operational security. Once a participant has been entered into this system, they are given a unique study identification number (ID). Any datasets and computer files that leave the firewall are stripped of all identifiers and individuals are referred to by their study ID. The study ID is also used on all analytical files.

Data will only be transferred through DriveID, Cellcontrol, Penn's Way to Health IT Platform, and the CHOP and Penn study teams. Data will be stored on secure servers both at

CHOP and Penn. Any data transferred between the CHOP and Penn study teams will be transferred via encrypted hard drive or secure email.

